Project Title: Cognitive Adaptations to Reduce Emotional Stress Associated with Type 1 Diabetes

NCT Number: NCT03698708

Date: 10/4/2021

Study 2. Develop a preventative behavioral intervention for families of school-agers with T1DM.

Current Research Design. We will recruit families to participate in a small pilot trial a video-based telehealth intervention to reduce diabetes distress, depressive symptoms, and hypoglycemia fear in parents of school-age children with type 1 diabetes. Diabetes distress comprises a constellation of negative psychological symptoms that may make it harder for children and parents to manage type 1 diabetes, leading to suboptimal health outcomes for children. There are promising examples of treatments to reduce diabetes distress for mothers of adolescents with type 1 diabetes and in adults with type 1 diabetes, but no interventions targeting parents of school-age children with type 1 diabetes specifically.

Objective: To compete a pilot trial of a new video-based telehealth intervention to reduce diabetes distress, depressive symptoms, and hypoglycemia fear in parents of school-age children with type 1 diabetes.

Subjects. We will recruit eligible families from the Diabetes Center at Children's Mercy-Kansas City (CMH). All families regardless of gender, race, ethnicity, and socioeconomic class will be considered potentially eligible to participate.

Family Inclusion Criteria are:

1. families with a child with T1DM between the ages of 5 and 12 years old,
2. T1DM diagnosis within 12 months of enrollment,
3. child using either basal/bolus or insulin pump therapy,

Family Exclusion Criteria are:

1. current involvement in foster care,
2. evidence of type 2 or monogenic diabetes,
3. the presence of severe psychiatric disorders or comorbid chronic conditions (e.g., renal disease) that require ongoing care beyond T1DM,
4. chronic use of medications that may impact glycemic control (i.e., systemic steroids),
5. a diagnosis of developmental delay,
6. non-English speaking families (the proposed study surveys are currently only available in English).

Procedure. Clinic staff will identify eligible families and research team members will recruit families. Once informed consent is obtained, parents will complete a demographic questionnaire. Families will complete a baseline assessment visit (viz., adherence measures and HbA1c kit) before the first treatment session. Following completion of treatment, families will complete a post-treatment assessment. Families will receive \$40 each for completing the baseline and post-treatment assessments (total \$80).

Outcome Measures. Primary outcome measures will be: parents' diabetes distress, depressive symptoms, and hypoglycemia fear. Secondary outcome measures will be the Feasibility and Acceptability the new treatment.

Diabetes Distress. We will use the Problem Areas in Diabetes-Parent Report (PAID-PR). This is a validated 18-item measure of diabetes distress with higher scores suggesting greater distress. Scores can range 0-72.

Depressive Symptoms. We will use the Center for Epidemiological Studies Depression Scale-Revised (CESD-R). This is a validated 20-item measure of depressive symptoms with higher scores suggesting more depressive symptoms occurring over the past 2 weeks. Scores can range 0-60.

Hypoglycemia Fear. We will use the Hypoglycemia Fear Survey for Parents (HFS-P). This is a validated 25-item measure of hypoglycemia fear with higher scores suggesting more fear. Scores can range 25-125.

Treatment Satisfaction. We will use a study specific 15-item survey to assess for treatment satisfaction. Survey scores can range from 15-75, with higher scores suggesting greater satisfaction/acceptability.

Hypothesis.

Hypothesis 1. Parents who participate in our new intervention will report lower diabetes distress post-treatment and at three-months follow-up.

Hypothesis 2. Parents who participate in our new intervention will report reduced depressive symptoms and hypoglycemia fear post-treatment and at three-months follow-up

Hypothesis 3. Our intervention will be feasible, meaning that it would exhibit an attrition rate of <25% of families and a group attendance rate of >85% of all telehealth sessions.

Data Analysis: To test Hypothesis 1, we used a series of repeated measures analysis of variance (ANOVA) models with parent group (8- versus 12-sessions) as a between-subject variable, time as a within-subject variable, and parents' diabetes distress score as the dependent variable. We used separate models to test for treatment effects between parents' pre- and post-treatment diabetes distress scores and between parents' pre- and 3-months follow-up distress scores (maintenance effect). To test for treatment effects in Hypothesis 2 (i.e., parents' depressive symptoms and hypoglycemia fear scores), we used a similar analytical approach. We will use descriptive statistics to test for Hypothesis 3.

Power Analysis: A sample of 12 families may not have sufficient power for the exploratory analyses. But this sample is sufficient to (1) obtain estimated effect sizes for the exploratory outcomes, which can be used to power a larger clinical trial; and (2) assess initial feasibility/acceptability of the intervention.

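### Does the absence of the three-month assessment from the Procedure leave half of Hypotheses 1 and 2 untestable?

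*Combined protocol and SAP*

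**What the plan says.** The Procedure gives two assessments in order. The first is at baseline: "Families will complete a baseline assessment visit (viz., adherence measures and HbA1c kit) before the first treatment session". The second comes after treatment: "Following completion of treatment, families will complete a post-treatment assessment". The payment is $40 each "for completing the baseline and post-treatment assessments", $80 in total.

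Outcome Measures sets the endpoints: "Primary outcome measures will be: parents' diabetes distress, depressive symptoms, and hypoglycemia fear". These are measured by the PAID-PR, CESD-R and HFS-P.

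Both efficacy hypotheses look beyond the end of treatment. Hypothesis 1 reads "Parents who participate in our new intervention will report lower diabetes distress post-treatment and at three-months follow-up". Hypothesis 2 reads "Parents who participate in our new intervention will report reduced depressive symptoms and hypoglycemia fear post-treatment and at three-months follow-up".

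Data Analysis describes repeated measures ANOVA with session group (8 or 12) as the between-subject factor. Separate models compare baseline with post-treatment and baseline with three months, and the second is labelled as testing maintenance. The outcomes of Hypothesis 2 are handled in a similar way. The models for Hypotheses 1 and 2 are described in the past tense. No section gives a visit window for the three-month score or says from which event the three months run.

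**The concern.** Read alone, the Procedure ends at the post-treatment assessment, and the payment sentence seems to confirm that only two exist. A team that took that paragraph as its full instructions would have no three-month score, and the follow-up part of Hypotheses 1 and 2 could not be tested for any of the three primary outcomes.

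The missing anchor adds to the worry. The groups have 8 and 12 sessions, so three months counted from baseline would fall at a different distance from the end of treatment in each group. Group is a factor in the model, so its effect could then be mixed with time since treatment. Timing also decides what is measured: the CESD-R is described as reflecting "more depressive symptoms occurring over the past 2 weeks".

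The Power Analysis section says the pilot should supply effect sizes for a larger trial. A maintenance effect at an undefined time would be hard to reuse for that.

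**Working it through.** **1. The plan's own figure.** The total payment is the only stated figure that depends on the number of assessments. Two assessments × $40 = $80, which matches. The payment sentence therefore covers baseline and post-treatment only.

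**2. Time points.** Analysed: baseline, post-treatment, three months. Described in the Procedure: baseline, post-treatment. The difference is three months, so 1 of 3.

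**3. Models affected.** There are three outcomes (diabetes distress, depressive symptoms, hypoglycemia fear) and two contrasts each (pre-post and pre-three-month), so 3 × 2 = 6 models, of which 3 use the three-month score. This takes the similar approach for Hypothesis 2 to mean both contrasts. That is the natural reading, because Hypothesis 2 itself names three months.

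**4. Is the Procedure meant as a complete schedule?** Count the primary surveys that it names: 0 of 3. Its only list of contents is adherence measures and an HbA1c kit at baseline. If silence in the Procedure meant that something was not done, no primary outcome would be measured at any time, baseline included. That cannot be the intent. Measures and time points have to be read from the whole short document, which names the three-month follow-up three times: in Hypothesis 1, in Hypothesis 2 and in Data Analysis.

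**5. Which anchor fits the text?** The session frequency is not stated, so I assume weekly or two-weekly sessions and take three months as 13 weeks.

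| Sessions | Frequency (assumed) | Treatment ends (week) | Three months from baseline, relative to treatment end | Three months from treatment end (week) |
|---|---|---|---|---|
| 8 | weekly | 8 | 13 − 8 = 5 weeks after | 8 + 13 = 21 |
| 12 | weekly | 12 | 13 − 12 = 1 week after | 12 + 13 = 25 |
| 8 | two-weekly | 16 | 13 − 16 = −3, so 3 weeks before | 16 + 13 = 29 |
| 12 | two-weekly | 24 | 13 − 24 = −11, so 11 weeks before | 24 + 13 = 37 |

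Counted from baseline, the follow-up would come 1 or 5 weeks after treatment, or before treatment had finished. The two-weekly case cannot be a follow-up at all, and one week after treatment is a poor test of maintenance. Counted from the end of treatment, each group has the same 13 weeks. Both the maintenance label and the order of the time points in the hypotheses fit that reading.

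**6. What else depends on it?** The 12 families are not derived from a significance level, power or effect size, so no sample-size figure moves. The pre-post models use the two time points that the Procedure does describe.

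**The case for a change.** The strongest case for a change is that the Procedure reads as complete, the $80 is fully accounted for, and the scores left out belong to primary outcomes and support half of the models. The past tense does not settle whether data were collected, since Data Analysis mixes tenses (Hypothesis 3 is still in the future). Families who leave early have no completion of treatment to count from. Hypothesis 3 hopes that "it would exhibit an attrition rate of <25% of families". With 12 families, 2/12 = 16.7% meets that target and 3/12 = 25.0% does not, so even a trial that meets it could have two such families.

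Part of this stands. The sections do not match, the anchor is implied but not written, and there is no window.

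The rest carries less weight. The payment sentence says what is paid for, not everything that is done. Recall over two weeks applies at every time point, including the post-treatment assessment, which has no window either, and no figure shows that a shift in timing would alter a conclusion. Whether to follow families who stop treatment, and up to when attrition is counted, are separate questions that this mismatch does not raise. The remedies that would alter the trial (new collection, or removal of the three-month models) make sense only if the data are absent, and the documents do not show that.

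**Conclusion.** No change to the plan follows. The Procedure leaves out 1 of 3 analysed time points, which feeds 3 of 6 models, but the hypotheses and analysis supply it. A team following the whole plan would collect the score, and an analyst would count the three months from the end of treatment. An added sentence in the Procedure would tidy the record without altering an estimate, the 12 families or the pre-post results. In a pilot meant to give effect sizes and to assess feasibility, this is a gap that the team fills sensibly by reporting when the follow-up scores were taken.

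The conclusion rests on two readings: that three months means after treatment, and that the past-tense account reflects models fitted to collected data. Both are the natural readings, but neither is stated outright. If no three-month scores had been collected, the follow-up parts of Hypotheses 1 and 2 could not be tested; nothing in the documents points that way.

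### Does Hypothesis 3 need a stated attrition time point and a rule for dropouts' sessions before feasibility can be judged?

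*Combined protocol and SAP*

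**What the plan says.** Hypothesis 3 defines feasibility by two strict cut-offs: "it would exhibit an attrition rate of <25% of families and a group attendance rate of >85% of all telehealth sessions". Its analysis is one sentence in the Data Analysis section: "We will use descriptive statistics to test for Hypothesis 3". Outcome Measures lists feasibility as a secondary outcome. The Power Analysis section makes an initial look at feasibility and acceptability one of its two reasons why 12 families are enough.

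The plan mentions two later time points. The Procedure has the first: "Following completion of treatment, families will complete a post-treatment assessment". Its payments are "each for completing the baseline and post-treatment assessments", and it mentions no later visit. Hypothesis 1, by contrast, expects that parents "will report lower diabetes distress post-treatment and at three-months follow-up". Hypothesis 2 also covers both times, and the Data Analysis section has a separate maintenance model for the three-month scores. The models are fitted "with parent group (8- versus 12-sessions) as a between-subject variable", so families do not all have the same number of sessions. The split of the 12 families between the two groups is not given.

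**The concern.** A criterion stated as a cut-off needs a numerator, a denominator and a time. Hypothesis 3 gives the cut-offs and leaves part of the rest open.

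- **Attrition.** A family that completes the post-treatment assessment but not three months is retained on one reading and lost on the other.
- **Attendance.** A family that leaves halfway has sessions it could no longer attend. These can count as missed or be left out, or the family can be dropped from the calculation altogether.
- **Pooling.** Nothing says how the 8- and 12-session groups are combined.

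If the readings disagree, a choice made after seeing the data could decide whether the intervention is called feasible. Leaving dropouts out also tends to flatter attendance. The matter seems to carry weight because the plan concedes that power may be insufficient for the exploratory analyses and rests part of its case for 12 families on feasibility.

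**Working it through.** The plan gives no feasibility result or derivation to reproduce. The check is whether the readings can disagree, and then which reading the text favours.

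**Inputs from the plan:** 12 families; 8 or 12 sessions by group; attrition strictly below 25%; attendance strictly above 85%.

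**Assumed inputs:** six families per group, so 6 × 8 + 6 × 12 = 120 scheduled sessions. One family leaves each group halfway, having attended every session until then (4 + 6 = 10). The ten retained families are offered 5 × 8 + 5 × 12 = 100 sessions and attend 90.

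**Attrition = families lost / 12**

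- Two lost: 2/12 = 16.7%, met.
- Three lost: 3/12 = 25.0%, missed, because the cut-off is strict.

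So one further family lost between the end of treatment and three months reverses the result. The chance of passing at the end of treatment and failing at three months is P(X ≤ 2) at the earlier cumulative rate minus P(X ≤ 2) at the later one, with X binomial and n = 12. P(X ≤ 2) is 0.889, 0.736, 0.558 and 0.391 at 10, 15, 20 and 25%. For assumed rates rising from 10 to 15%, 10 to 20%, 15 to 20% and 15 to 25%, the chance is about 15, 33, 18 and 35%.

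**Attendance = sessions attended / sessions counted**

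| Reading | Calculation | Above 85%? |
|---|---|---|
| All scheduled sessions | (90 + 10)/120 = 83.3% | No |
| Sessions after departure removed | (90 + 10)/(100 + 10) = 90.9% | Yes |
| Dropouts removed entirely | 90/100 = 90.0% | Yes |

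Let x be the number of the 100 sessions that retained families attend.

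- All scheduled: (x + 10)/120 > 0.85 needs x ≥ 93.
- Later sessions removed: (x + 10)/110 > 0.85 needs x ≥ 84.
- Dropouts removed: x/100 > 0.85 needs x ≥ 86.

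The all-scheduled result therefore differs from the second reading for x = 84 to 92, and from the third for x = 86 to 92. More generally, if attendance while enrolled is 90%, the all-scheduled rate falls to 85% once 1 − 0.85/0.90 = 5.6% of scheduled sessions come after a departure. Of 120 sessions, that is 7.

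**Pooling.** This matters less. With 46/48 in one group and 56/72 in the other, the pooled rate is 102/120 = 85.0% (missed). The mean of the family rates is (95.8 + 77.8)/2 = 86.8% (met). The example was chosen to land on the cut-off.

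**What the text favours.** Hypothesis 3 takes its attendance percentage over every telehealth session, without restriction. Either alternative needs an exclusion the plan does not contain. For attrition, Hypotheses 1 and 2 each name three months and Hypothesis 3 does not. Hypothesis 3 also pairs attrition with session attendance, and the Procedure's last assessment is the post-treatment one. These features point to all scheduled sessions and to loss over the treatment period. They fall short of an explicit definition.

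**The case for a change.** The best case for a change is that Hypothesis 3 states a pass/fail definition of feasibility, and such a claim should not depend on a denominator picked afterwards. A simulation gives that some weight. With attrition of 10 to 20%, attendance while enrolled of 88 to 95%, independent families and a random exit session, the Hypothesis 3 result differed in 11 to 35% of trials between leaving dropouts out and counting all scheduled sessions. In every disagreement, leaving them out was the reading that passed. A clarifying sentence would need no extra families or data.

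The ambiguity stands, and so does its direction. Three things limit it.

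- The simulation inputs are not in the plan. They show that a reversal can happen, not how likely it is here. They also compare the natural reading of the attendance criterion with one the text does not suggest.
- The plan makes no go/no-go decision depend on Hypothesis 3. It claims an initial assessment in a small pilot, and says that effect-size estimates, not the feasibility result, may be used to power a larger trial.
- The attrition cut-off separates little at this size. The exact 95% interval for 2/12 is 2.1% to 48.4%, so fixing the time point would not turn a pass into firm evidence that attrition is below 25%.

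A new definition might also come too late to be prospective. The Data Analysis section says of Hypothesis 1 that "we used a series of repeated measures analysis of variance (ANOVA) models", although its sentence on Hypothesis 3 is in the future tense. If the feasibility data had been seen, a definition written now would be post hoc.

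**Conclusion.** No change follows. Hypothesis 3 leaves the attrition time point and the treatment of dropouts' sessions unstated. With 12 families the result can turn on one family (16.7% against 25.0%) or on the denominator (83.3% against 90.9% or 90.0%). The attendance figures rest on an assumed equal split, two halfway dropouts and 90% attendance among retained families.

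This is missing detail, not an error. No figure in the plan is wrong, the readings the text favours are sound, and a descriptive analysis would ordinarily report how many families left, when, and how many sessions were attended. From those counts a reader can work out each version.

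The Procedure's silence on a three-month assessment that Hypotheses 1 and 2 need is a separate matter. It concerns those hypotheses and does not make the feasibility criterion unusable.

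### Does judging feasibility against single limits, when the analysis has 8- and 12-session groups, require a change to the plan?

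*Combined protocol and SAP*

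**What the plan says.** The Current Research Design section opens with "We will recruit families to participate in a small pilot trial a video-based telehealth intervention". Neither it nor the Procedure section gives a number of sessions, a second version, a method of allocation or group sizes.

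The Data Analysis section, under Hypothesis 1, uses repeated measures ANOVA "with parent group (8- versus 12-sessions) as a between-subject variable, time as a within-subject variable". For Hypothesis 2 it says "we used a similar analytical approach".

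Hypothesis 3 defines feasibility by two limits: "it would exhibit an attrition rate of <25% of families" and "a group attendance rate of >85% of all telehealth sessions". Its whole analysis is one sentence: "We will use descriptive statistics to test for Hypothesis 3".

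The Power Analysis says "A sample of 12 families may not have sufficient power for the exploratory analyses", but calls the same sample enough to "assess initial feasibility/acceptability of the intervention".

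**The concern.** The two session groups appear only in a parenthesis of the Data Analysis section. The ANOVA keeps them apart; Hypothesis 3 has no corresponding term. If all families are put into one rate, two things can happen.

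- A pooled pass may include one session group that misses the limit.
- Attendance over all scheduled sessions and attendance averaged over families are identical when every family has the same number of sessions. With 8 sessions for some and 12 for others they can differ, and so could the verdict.

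Hypothesis 3 is the only hypothesis with numeric pass marks, and the low-power caveat is worded for the exploratory analyses, not for feasibility. A team planning a larger trial might therefore take a feasible verdict as applying to a session number that did not earn it.

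**Working it through.** **Inputs.** From the documents: 12 families (Power Analysis); limits of <25% and >85% (Hypothesis 3); 8 or 12 sessions (Data Analysis). The sample of 12 is asserted without a calculation, so there is no figure to reproduce. Group sizes are not given. I assume 6 v 6 and show 4 v 8 and 8 v 4 (8-session group first) where it matters. All scheduled sessions count.

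**Attrition, pooled.** 2/12 = 16.7% passes and 3/12 = 25% does not, so at most two losses are allowed. At 6 v 6, zero or one loss cannot put a group at 25% or more (1/6 = 16.7%). Two losses do so only if both fall in one group: 2/6 = 33.3%. Given exactly two losses placed at random, the chance is 2 × C(6,2)/C(12,2) = 30/66 = 45%.

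That 45% is conditional on two losses. With the same true attrition p in both groups, the share of pooled passes containing a group at 25% or more is

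30p²(1−p)¹⁰ / [(1−p)¹² + 12p(1−p)¹¹ + 66p²(1−p)¹⁰].

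| True attrition, both groups | Pooled pass | Pass with a group at ≥25% | Share of passes |
|---|---|---|---|
| 5% | 0.980 | 0.045 | 4.6% |
| 10% | 0.889 | 0.105 | 11.8% |
| 15% | 0.736 | 0.133 | 18.1% |

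If the groups truly differ, the share is larger: with 5% in one and 30% in the other, 64.8% of trials pass and 37% of those passes contain such a group.

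**Attendance, pooled.** At 6 v 6 there are 6 × 8 + 6 × 12 = 120 family-sessions, and >85% needs 103.

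- Lowest possible with the other group at 100%: (103 − 72)/48 = 31/48 = 65% for 8 sessions, or (103 − 48)/72 = 55/72 = 76% for 12 sessions. At 4 v 8 these are 41% and 80%; at 8 v 4, 75% and 67%.
- Less extreme: 95% (8-session) and 80% (12-session) pool to (48 × 0.95 + 72 × 0.80)/120 = 86.0% at 6 v 6 and 89% at 8 v 4, both passes. At 4 v 8 they pool to 84%, which fails, so nothing is hidden there.

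**Choice of attendance formula.** 46/48 and 56/72 give 102/120 = 85.0% over sessions (not >85%), but (46/48 + 56/72)/2 = 86.8% averaged over families (pass). One more attended session, 46/48 and 57/72, gives 103/120 = 85.8% and 87.5%, and both pass.

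**What a group-level miss would tell the reader.** The exact 95% CI is 4.3% to 77.7% for 2/6 and 2.1% to 48.4% for 2/12. For attendance, simulation at 6 v 6 with both groups at a true 88% put at least one group at or below 85% in 26.5%, 30.1% and 31.7% of pooled passes, for within-family correlation of 0, 0.1 and 0.2. A group-level miss is therefore common even when the two groups are identical.

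**The case for a change.** The best case for a change is this. The omission is in the text and is not a redaction. Without knowing how families came to have 8 or 12 sessions, a reader cannot interpret the between-group term. The power caveat does not cover feasibility. A larger trial must deliver a definite number of sessions, and the plan does not tie its feasibility verdict to either number. The remedy would cost a paragraph and a small table, with no new data.

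Part of this stands. The design sections and the Data Analysis section do not match, and a report of the trial should describe both groups, their sizes and how families entered them.

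The rest is weaker. The plan nowhere says the groups are combined for Hypothesis 3. Descriptive statistics can be given by group, and the wording of the attendance limit can be read as per group, although the attrition limit gives no such hint. None of the three hypotheses compares 8 with 12 sessions, so none depends on how families were allocated. For Hypotheses 1 and 2 the time effect is the evident test, and a model with a group factor already gives change by session group, so effect sizes can be tied to a session number. The lowest attendance figures need the other group to be perfect, and the conflict between formulas needs a total of exactly 85.0%.

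**Conclusion.** No change to the plan follows. The plan omits a description of the two session groups and does not say whether feasibility is judged overall or by group. That is missing detail; no stated rule has been shown to give a wrong answer. An overall verdict is a reasonable way to judge initial feasibility in 12 families, and an analyst can set out attrition and attendance counts by session group beside it under the plan as written.

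Masking is possible at every split examined, from 2/10 to 6/6 for attrition. At 6 v 6 with equal true attrition of 5% to 15% it affects about 5% to 18% of pooled passes, and more if the groups truly differ. Group rates reported as estimates would not alter the overall verdict. Separate pass marks would often be missed by chance: in about 26% to 32% of pooled passes on attendance when both groups are at a true 88%. These figures rest on the assumed group sizes and true rates, which the documents do not give.

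### Twelve families, all treated, cannot supply a treatment effect size for powering a larger trial; the pilot gives only an imprecise within-family change

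*Combined protocol and SAP*

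**What the plan says.** The Power Analysis section opens with a concession: "A sample of 12 families may not have sufficient power for the exploratory analyses". It then states without qualification that the same sample is adequate for two purposes. One is an initial look at feasibility and acceptability. The other is to "obtain estimated effect sizes for the exploratory outcomes, which can be used to power a larger clinical trial".

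The Data Analysis section gives the model as a repeated measures ANOVA with "parent group (8- versus 12-sessions) as a between-subject variable, time as a within-subject variable". It describes its purpose this way: "We used separate models to test for treatment effects between parents' pre- and post-treatment diabetes distress scores". A second model does the same for change from baseline to three months, and Hypothesis 2 is handled similarly.

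Hypothesis 1 names no comparator: "Parents who participate in our new intervention will report lower diabetes distress post-treatment and at three-months follow-up". The Family Inclusion Criteria require "T1DM diagnosis within 12 months of enrollment". Hypothesis 3 defines feasibility partly by whether "it would exhibit an attrition rate of <25% of families". No control group, SD, pre-post correlation, precision target or method of assignment to 8 or 12 sessions appears anywhere.

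**The concern.** Supplying effect sizes for the next trial is one of only two reasons given for the sample size, so it matters whether the design can do it.

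A larger trial is normally powered on a difference between arms. Here the only between-family factor is 8 versus 12 sessions, and both groups are treated. The time effect mixes the intervention with everything else that moves parents' scores in the period after a child's diagnosis, including adjustment and regression to the mean. The group-by-time term is a true between-group comparison, but it estimates 12 sessions against 8, not the intervention against none. Calling the time effect a treatment effect therefore claims more than the design can show.

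Imprecision is a separate problem. It does not decide whether the change is causal, but it does decide whether the estimate could serve alone as a planning value even if there were no background change.

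If the figure is carried forward as it stands, the next trial could be too small or too large, and the pilot cannot show which.

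**Working it through.** **Inputs from the document.** There are 12 families in total (Power Analysis). The groups are 8 and 12 sessions (Data Analysis). The attrition limit is 25% (Hypothesis 3), so 9 completers, 12 × 0.75, is the edge of that limit. The document gives no derivation of 12 and no precision target, so there is no planned figure to reproduce. What can be computed is the precision that 12 families provide.

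**Assumed for illustration (not in the document).** Observed standardised improvement 0.5; pre-post correlation r from 0.3 to 0.8 with equal SDs; 6 families per group; background change of 0.2 SD either way; later trial two-arm, 80% power, two-sided 0.05.

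**1. Precision of the mean change,** in SDs of the change score: half-width = t(0.975, n−1)/√n.
- n = 12: 2.201/3.464 = 0.64 (0.635 before rounding)
- n = 9: 2.306/3 = 0.77
- n = 12 with the two-group model's 10 error df: 2.228/3.464 = 0.64 (0.643)

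These depend only on n. In raw-score SDs at n = 12, multiply 0.635 by √(2(1−r)): 0.75 at r = 0.3, 0.64 at 0.5, 0.49 at 0.7, 0.40 at 0.8.

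**2. 95% CI for an observed standardised change,** by inverting the noncentral t distribution.

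| Observed change | Completers | 95% CI |
|---|---|---|
| 0.5 | 12 (11 df) | -0.11 to 1.09 |
| 0.5 | 12 (10 df) | -0.12 to 1.09 |
| 0.5 | 9 (8 df) | -0.21 to 1.18 |
| 0.8 | 12 (11 df) | 0.13 to 1.44 |
| 1.0 | 12 (11 df) | 0.29 to 1.69 |

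**3. Implied size of the later trial** if the change is used as a between-arm effect on change scores (two-sample t test).
- 0.5 gives 64 per arm; the upper limit 1.09 gives 15; the lower limit is below zero and gives no finite size.
- For an observed 0.8, the unrounded limits give 9 to 909 per arm. For 1.0 they give 7 to 195. The normal approximation gives one fewer per arm in each case.

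**4. Choice of standardisation.** If the later trial compares final scores, d = 0.5 × √(2(1−r)).
- r = 0.3: 0.592, 46 per arm
- r = 0.7: 0.387, 106 per arm
- r = 0.8: 0.316, 158 per arm

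The plan does not say which SD its effect size would use.

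**5. Missing comparator.** Suppose 0.5 is observed and the later trial enrols 64 per arm.
- Untreated parents would improve by 0.2 SD: contrast 0.5 − 0.2 = 0.3, power 39%.
- No background change: contrast 0.5, power 80%.
- Untreated parents would worsen by 0.2 SD: contrast 0.5 + 0.2 = 0.7, power 98%.

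**6. The one between-group contrast available,** 8 versus 12 sessions at 6 per group: half-width = t(0.975, 10) × √(1/6 + 1/6) = 2.228 × 0.577 = 1.29 SD of change.

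**The case against.** The best defence is that the plan is already modest. It calls itself a small pilot, admits low power, labels the outcomes exploratory, and says only that the effect sizes can be used later, not that they will be the sole input. The hypotheses predict lower scores among participants and claim no comparison. This limits the point to what the estimate can do by itself. It does not remove the point: the admission of low power concerns testing, while the statement about effect sizes is separate and unqualified, and the plan names no other input and no safeguard.

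A second objection is that the starkest figures depend on chosen inputs. An unbounded trial size follows from taking 0.5; with 12 completers the lower limit is above zero from an observed change of about 0.65. That is fair, but 0.8 still spans 9 to 909 per arm, and the half-widths in step 1 need no assumed effect. Likewise, 9 completers would just miss a target of under 25%. With 10, the most attrition inside the target, the half-width is 2.262/√10 = 0.72, which is little better.

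Third, the plan does not say whether the time effect or the group-by-time effect would be carried forward. Reading it as the time effect is an interpretation, but the alternative is less precise (1.29 SD) and answers a different question.

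**Conclusion.** The concern holds and should be fixed. The statement that 12 families are adequate to give effect sizes for powering a larger trial is wrong as written, and so is the label given to the pre-post and pre-to-three-month changes in the Data Analysis. The missing untreated comparator is why the change is not a treatment effect. The imprecision is why, even taken as a within-family change, it cannot size a trial alone.

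The half-widths of 0.64 and 0.77 SD of change rest only on the document's own figures. The per-arm sizes and power values rest on the assumed effect, correlations, background change and even split, and they illustrate scale rather than forecast it. The direction of the bias is unknown. The feasibility purpose of the sample is not affected by this point.

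**What to change.** In the Power Analysis, replace the first stated use of the sample with text such as:

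> The pilot will estimate outcome SDs, pre-post correlation and retention, each with a confidence interval. Pre-post and pre-to-3-month change will be reported with 95% CI as within-family change, not as a treatment effect. This change will not by itself be the effect size for the larger trial, which will be powered on a justified between-arm difference with a cautious SD (for example, an upper confidence limit).

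In the Data Analysis, refer to change over time wherever the text now speaks of treatment effects.

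**Cost.** Wording and a few descriptive estimates. Sample size, ANOVA model, visits and burden on families are unchanged. The plan makes a less favourable claim, and the later trial needs its own justification for the between-arm difference.

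An SD from 12 families is also uncertain, so the level of any upper limit should be stated. With 11 df, the upper end of a two-sided 95% interval is 1.70 times the estimated SD, which multiplies the later sample size by about 1.70² = 2.9. A one-sided 80% limit multiplies it by about 1.6.
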